5.9. Withdrawal criteria

Participants with Stroke

It will be explained to the potential participant that entry into the study is entirely voluntary and that their treatment and care will not be affected by their decision. Participants will be informed that they can withdraw from the study at any given point and that this will not affect their rehabilitation or healthcare provision. Should participants withdraw the data collected so far will not be destroyed and will be used in the analysis. All data will be anonymous and identification will not be possible.

Participants may discontinue their allocated intervention or withdraw from the study for the following reasons:

- withdrawal of consent.
- changes to their health status preventing their continued participation,
- failure to adhere to protocol requirements.
- Participant re-gains capacity and they choose to withdraw from the study

Caregivers

It will be explained to the potential participant that entry into the study is entirely voluntary and that their or the person with stroke they support's treatment and care will not be affected by their decision. The caregiver can decline to take part with no impact on the participant with stroke continuing with the study. Participants will be informed that they can withdraw from the study at any given point and that this will not affect their care or the rehabilitation or healthcare provision of the participant with stroke. Should participants withdraw the data collected so far will not be destroyed and will be used in the analysis. All data will be anonymous, and identification will not be possible.

Clinicians

It will be explained to the potential participant that entry into the study is entirely voluntary and that their ability to continue to support participants with stroke to use the SNMES will not be impacted nor will their decision impact on their job role/employment. Participants will be informed that they can withdraw from the study at any given point and that this will not affect their ability to continue to support participants with stroke to use the SNMES will not be impacted nor will their decision impact on their job role/employment. Should participants withdraw the data collected so far will not be destroyed and will be used in the analysis. All data will be anonymous, and identification will not be possible.

All Participants

Participants may be withdrawn from the trial either at their own request or at the discretion of the Investigator. The participants will be made aware that this will not affect future care, care of their loved one, or their job role/employment. Participants will be made aware (via the information sheet and consent form) that should they withdraw the data collected to date cannot be erased and may still be used in the final analysis.

However, if a participant indicates a wish to withdraw attempts should be made to see if the participant would permit at least primary outcome data to be collected (ideally at the end of the participant's follow-up period), ensuring that enough data are recorded to support the

STIM-STROKE Protocol v1.0 30-04-2025

IRAS ID: 332116 Page **49** of **70**

planned analysis. Participants should not be accepted as lost to follow-up unless phone calls, letters or visits to the participant and next of kin have been fruitless.

Enrolled participants who withdraw and were not yet randomised will be replaced (though the withdrawn participant will keep their trial ID). Participants who withdraw after randomisation will not be replaced.

5.10. End of trial

The activity used to define the end of the study will be the end of the analysis for the quantitative and qualitative study work packages.

6. SAFETY REPORTING

6.1. Definitions

6.1.1. Adverse Event

An AE (Adverse Event) is any untoward medical occurrence in a subject, including occurrences which are not necessarily caused by or related to the study intervention. An AE can therefore be any unfavourable and unintended sign (including an abnormal laboratory finding), symptom or disease temporally associated with study activities.

Examples of adverse events that can occur due to electrical stimulation are:

- Skin redness, irritation, or rash at electrode site or from the brace
- Muscle soreness
- Muscle spasm
- Musculoskeletal injury
- Fatique
- Muscle strain
- Joint paint

6.1.2. Serious Adverse Event (SAE) and Serious Adverse Device Effect (SADE)

An SAE is any untoward medical occurrence that fulfils at least one of the following criteria:

- Is fatal results in death (NOTE: death is an outcome, not an event)
- Is life-threatening (an event in which the participant was at risk of death at the time of the event; not refer an event which hypothetically might have caused death if it were more severe)
- Requires inpatient hospitalisation or prolongation of existing hospitalisation
- Results in persistent or significant disability/incapacity
- Is a congenital anomaly/birth defect
- Is otherwise considered medically significant by the Investigator (either jeopardising the participant or requiring an intervention to prevent one of the above consequences)

The following cases of hospitalisation are not considered 'serious':

STIM-STROKE Protocol v1.0 30-04-2025

IRAS ID: 332116 Page **50** of **70**

- Routine treatment or monitoring of the studied indication not associated with any deterioration in condition.
- Treatment, which was elective or pre-planned, for a pre-existing condition not associated with any deterioration in condition, e.g., pre-planned hip replacement operation which does not lead to further complications.
- Any admission to hospital or other institution for general care where there was no deterioration in condition.
- Treatment on an emergency, outpatient basis for an event not fulfilling any of the definitions of serious as given above and not resulting in hospital admission

Examples of Serious Adverse Events

- Myocardial infarction
- Additional Stroke
- TIA
- Deep Vein Thrombosis
- Pulmonary Embolism
- Chest infection
- Pressure sores/skin breakdown related to the leg brace or using the electrical stimulation
- Falls
- Seizures

6.1.3. Suspected Unexpected Serious Adverse Reaction (SUSAR)

An Adverse Event that fulfils at least one of the criteria of Serious and is possibly related to the conduct of the trial and/or use of either of the devices. No such events are anticipated and, therefore, all will be considered unexpected.

6.1.4. Investigators Assessment

Medical judgement should be exercised in deciding whether an AE is serious in other situations. Important AEs that are not immediately life-threatening or do not result in death or hospitalisation but may jeopardise the subject or may require intervention to prevent one of the other outcomes listed in the definition above, should also be considered serious.

6.1.5. Seriousness

An appropriately delegated member of the research team is responsible for assessing whether the event is serious according to the definitions given in section 6.1.2.

6.1.6. Causality

The Investigator must assess the causality of adverse events using their clinical judgement of the event. This may take into account the safety information that was provided, timing, mechanism and factors considered relevant. A 'relatedness' assessment will be made against

This will be assigned to one of the following categories:

• **Unrelated**: the AE is not considered to be related to the device or study conduct.

STIM-STROKE Protocol v1.0 30-04-2025

IRAS ID: 332116 Page **51** of **70**

- **Possibly**: although a relationship to the device or study conduct cannot be completely ruled out, the nature of the event, the underlying disease, concomitant medication, or temporal relationship make other explanations possible.
- **Probably**: the temporal relationship and absence of a more likely explanation suggest the event could be related to the device or study conduct.
- **Definitely**: the known effects of the stent/procedure suggest that the device or study conduct is the most likely cause.

Causality should be determined by the PI in the first instance.

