2.3. Outcome measures/endpoints

Feasibility and feasibility measurement

As this is a feasibility study the primary outcomes of interest relate to aspects of feasibility and acceptability. A red, amber, green (RAG) system will be used to identify if the feasibility study should progress to a definitive trial. Section 7.3 Statistical Analysis Plan specifies the RAG system in more detail. The aspects of feasibility and acceptability that will be explored are:

STIM-STROKE Protocol v1.0 30-04-2025

IRAS ID: 332116 Page **18** of **70**

- 1. Interviews with people with stroke and their caregivers as well as focus groups with clinicians to explore their experiences and views about the acceptability of the SNMES intervention. Furthermore exploring/tracking adverse events and adverse reactions to treatment with SNMES (a common side effect of electrical stimulation is skin irritation from the electrode pads) will contribute to the determining the feasibility and acceptability of the intervention.
- 2. Study enrolment rates and screening (the number of patients who agree to take part of those eligible). Where possible reasons for not taking part will be recorded to help plan the definitive trial. Additionally. data will be collected on the time duration between hospital admission and randomisation.
- 3. Through a participant diary, records within the electrical stimulation machine, and participant/caregiver interviews we will estimate engagement with the protocol and explore reasons for low or non-engagement with the protocol/not achieving recommended dose. This will help the team to identify if the suggested dose is feasible and acceptable on a larger scale.
- 4. Through participant/caregiver interviews, therapist focus groups, and completeness of collected data explore the feasibility and acceptability of the outcome measures used. Acceptability of candidate outcomes measures and their variability to inform the selection of outcomes, including the primary outcome, for a definitive trial, likely to be the 10-Metre Walk Test.
- 5. The data collected (including those from the outcome measures and participant interviews, data completeness, and standard deviation estimates) will inform the sample size considerations and primary outcome measure for the definitive trial.

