Participants will use the SNMES to create a co-contraction of the anterior and posterior muscles, the muscles at the front and back of the thigh as well as the front and back of the cal. For example, the quadriceps and hamstrings will be stimulated together, and the gastrocnemius, soleus, and anterior tibialis will be stimulated together. This will reduce the treatment time and participant burden. Some participants may find it more comfortable to use without the knee or ankle brace which will make it easier for caregivers to support when the participant is discharged. Some participants may experience incontinence due to their stroke or co-morbidities, not needing to use a knee brace would help with hygiene. Participants will be offered a knee and ankle brace to use if they wish. The research team will collect data around the use of the knee and ankle brace to inform a future trial.

As this is a feasibility and pragmatic trial is it useful to collect data of how participants used the electrical stimulation and braces, what was helpful and what was a hinderance.

Participants will use the SNMES while laying or semi-laying in bed. Position during use of the SNMES will be collected and used to inform a future trial.

The SNMES treatment will be integrated into the rehabilitation of the patient after stroke.

Training and Education on how to use SNMES

The Project Manager or another member of the research team with expertise in electrical stimulation will provide in-person education and training to the therapy (physiotherapists, occupational therapists, and therapy assistants) and nursing teams (including health care assistants) who will be supporting the participants to carry out the SNMES protocol. The education and training will encompass:

- how to use the stimulation unit setting up the stimulator unit, carrying out the stimulation, turning off the stimulator unit
- electrode placement (finding the motor point on the muscle)
- putting on and taking off the leg brace and AFO
- electrode and stimulator unit storage
- technical support/trouble shooting.

STIM-STROKE Protocol v1.0 30-04-2025

IRAS ID: 332116 Page **27** of **70**

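### The causality scale in section 6.1.6 pools device and study conduct and borrows stent wording, so the rating alone does not identify adverse reactions to SNMES

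*Protocol*

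**What the plan says.** Section 6.1.6 introduces the rating with "A 'relatedness' assessment will be made against", and in the text available the sentence stops there. It continues with "This will be assigned to one of the following categories": Unrelated, Possibly, Probably and Definitely. The lowest means that "the AE is not considered to be related to the device or study conduct". The highest means that "the known effects of the stent/procedure suggest that the device or study conduct is the most likely cause". The site PI makes the judgement in the first instance.

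Section 6.1.3 defines a SUSAR as an event that meets a seriousness criterion and "is possibly related to the conduct of the trial and/or use of either of the devices". Section 6.1.1 gives seven examples of events that stimulation can cause, starting with "Skin redness, irritation, or rash at electrode site or from the brace".

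Section 2.3, item 1, makes these data part of the feasibility and acceptability outcome: "Furthermore exploring/tracking adverse events and adverse reactions to treatment with SNMES". On the braces, which are optional, section 5 adds: "The research team will collect data around the use of the knee and ankle brace to inform a future trial".

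**The concern.** The outcome in section 2.3 concerns reactions to one thing, SNMES. The only causality scale in the protocol asks a wider question: was the event caused by anything the trial supplied or did? A related event in the SNMES arm may come from the stimulator and electrodes, from a knee or ankle brace, or from a study assessment such as dynamometry, the chair stand or the walk test. The scale records the same word in each case.

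If it stays as written, the count of related events in the SNMES arm is not a count of SNMES reactions. The team would also lack a direct record of whether the brace or the stimulation was thought responsible, although brace data are gathered to shape the next trial. Once events are coded this way, separating the sources means going back to each event and judging it again.

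The stent phrase is a second defect. Read literally, an investigator has no basis for choosing 'Definitely', because its evidence is the known effects of something absent from the trial.

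**Working it through.** No formula or rate is involved, so the check sets the sections side by side.

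1. **Target of the scale (6.1.6).** Unrelated, Possibly, Probably and Definitely all name the device and the study's conduct together. That is 4 of 4 categories pooled. Each event goes into one category, so no second rating could separate the sources.

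2. **What counts as a device.** Section 6.1.6 uses the singular without a definition. Section 6.1.3 uses a word that implies two. Section 5 issues three items (stimulator unit, knee immobiliser, ankle foot orthosis) plus electrode pads. Section 6.3 logs deficiencies for stimulators, electrodes, knee immobiliser and orthosis. The counts do not agree.

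3. **Meaning of a related rating by arm.** Controls receive no stimulator or brace but attend every assessment (section 5, Control Group). For them, a related event can only mean study conduct. In the SNMES arm it can mean stimulation, brace or assessment.

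4. **Whether the event's name settles the source.** Of the seven examples in 6.1.1, only the skin item mentions a site, and it covers electrode and brace together. The other six are soreness, spasm, musculoskeletal injury, fatigue, strain and joint pain, and none names a site. That several of these can follow strength testing or repeated standing as well as stimulation is a judgement made here, not a statement in the protocol. One of the serious event examples in 6.1.2, on pressure sores and skin breakdown, likewise merges brace and stimulation.

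5. **Whether timing settles it.** Baseline assessment precedes randomisation (5.3), and Visit 4, at 6 months, falls well after the 12-week intervention. Events close to either can often be placed. In between, the schedule is 3 sessions a week for 12 weeks, 3 × 12 = 36 sessions, with assessments at 6 and 12 weeks. Section 6.5 has event data collected at Visits 2, 3 and 4. Timing therefore helps for many events, but less for those arising around Visits 2 and 3.

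6. **What else is recorded.**
   - Brace-use data show exposure, not cause. Brace and electrodes can be used in the same session.
   - The diary records sessions and how the participant felt. It makes no causal judgement.
   - Section 6.5 requires adverse reactions to be reported on a form of their own, but section 6.1 never defines an adverse reaction. The heading of 6.1.2 names a serious adverse device effect, while its text defines only a serious adverse event.
   - The deficiency log in 6.3 covers equipment faults, not the cause of events.

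Each source narrows the possibilities. None assigns an individual event of soreness, strain or joint pain to stimulation, brace or assessment.

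**The case against.** The strongest reply is that the rating is not the only safety information. Allocation is known, and both arms have the same assessments. A descriptive table by arm therefore shows the assessment background in controls, and the excess in the SNMES arm points to the intervention. The ban on statistical comparisons in section 7.3 does not stop such a table. Site-specific risks are listed in Appendix 1 with checks at weeks 6 and 12. The brace serves to hold the limb still during stimulation, so it can be viewed as part of the delivered package. The stent phrase looks like template carry-over, and the rest of that sentence still makes sense. No progression criterion in Table 3 uses adverse events.

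Most of this stands, and it rules out three stronger readings:

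- A reader might infer that SNMES reactions cannot be separated from other events. The documents do not support that, because the sources just listed give partial separation.
- A reader might infer that the study cannot report any SNMES reaction rate. That does not follow either. The contrast between arms gives an indirect estimate, and the event description will settle some cases, such as a rash at an electrode.
- A reader might infer that serious events would be missed. Section 6.1.3 covers trial conduct and devices jointly, so pooling there widens the net.

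The unfinished sentence in 6.1.6 also calls for caution. Its object may have been lost when the PDF was read, and it may have listed separate targets. The gap is therefore not claimed as an error. Even so, the four category definitions would remain pooled and the stent wording would remain wrong.

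The reply does not supply attribution for the individual event. The arm contrast covers the whole package with about 30 per arm and says nothing about brace versus stimulation. The package argument also sits poorly with a brace that is optional and studied in its own right.

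**Conclusion.** The point holds in a limited form. As worded, the scale pools its targets in all four categories, leaves the device undefined and rests its top category on an item that is not in the trial. Section 6.1.3 does not match the equipment issued. The rating therefore does not by itself deliver the SNMES-specific reactions that section 2.3 names, and the other data repair this only in part.

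The protocol gives no event rates, so no numerical size can be attached. The consequence is confined to the safety part of the first feasibility outcome and to what is learned about the braces. Recruitment, follow-up, adherence and the progression decision are unaffected. The change should be made before events are coded, but the design does not depend on it.

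The conclusion assumes that one category is recorded per event, as the text reads, and that no separate list of targets stood in the broken sentence. If such a list exists, the remaining faults are the category wording, the stent phrase and section 6.1.3.

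**What to change.** - **6.1.6, target:** finish the introductory sentence by naming the items rated. Rate relatedness on the same four levels separately for (i) stimulator and electrodes, (ii) knee or ankle brace, marked not applicable if unused, and (iii) study assessments and procedures.
- **6.1.6, wording:** in all four definitions, replace the pooled target, and in the top one the stent phrase, with the item being rated.
- **6.1.3:** name the stimulator, electrodes, knee immobiliser and ankle foot orthosis. Keep the joint scope, so that a serious event rated at least 'possibly' on any of (i) to (iii) still qualifies.
- **6.1:** define an SNMES adverse reaction as an event rated at least 'possibly' on (i), so that the reaction form in 6.5 has a definition behind it.
- **7.3:** summarise (i), (ii) and (iii) separately, by arm.

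Keep the new ratings with the PI, who already judges causality, so that research practitioners who are meant to be blinded (5.4) are not asked about the device.

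The cost is protocol wording, two extra fields on the event form and slightly more work per event.

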6.1.7. Expectedness

No Serious Adverse Events are anticipated therefore any that occur should be reported as Unexpected.

6.1.8. Severity

The Investigator must assess the severity of Serious Adverse Events according to the following terms and assessments. The intensity of an event should not be confused with the term "serious" which is a regulatory definition based on patient/event outcome criteria.

- Mild: Some discomfort noted but without disruption of daily life;
- Moderate: Discomfort enough to affect/reduce normal activity;
- Severe: Complete inability to perform daily activities and lead a normal life.

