1.1. Assessment and management of risk

Electrical stimulation is currently being used in routine care physiotherapy practice with minimal reports of adverse events. Electrical stimulation has been incorporated into best practice guidelines for people with stroke as well as people with Multiple Sclerosis. The risk associated with using electrical stimulation within this study is not different to using electrical stimulation within routine clinical practice.

Previous study of electrical stimulation report few adverse events. Common adverse events when they occur are skin irritation at the electrode site, muscle fatigue and soreness following electrical stimulation and joint pain.

Participants will be instructed to let the research team know if they experience any adverse events, these will be monitored as per Section 8 Safety Measures. If participants experience muscle soreness, muscle fatigue, joint pain, or skin irritation they will be supported by the research team to manage this to be able to continue in the study.

The benefits of using electrical stimulation are maintaining muscle bulk and size which will help to prevent atrophy, improved circulation at the stimulation site, and the time doing the stimulation will contribute to additional minutes of exercise which is recommended in the new Clinical Stroke Guidelines.

2. OBJECTIVES AND OUTCOME MEASURES/ENDPOINTS 2.1. Primary objective

The primary aims of this feasibility study are to i. assess the feasibility and acceptability of SNMES started within 2-weeks after stroke and applied for 12-weeks to the weakened lower limb muscles and ii.to provide necessary data to inform the design of a future definitive RCT testing whether SNMES started within two weeks after stroke prevents muscle wastage and improves recovery of strength, walking and quality of life in people with severe lower extremity weakness.

The primary feasibility and acceptability objectives are described below.

- 1. Determine the feasibility and acceptability of the SNMES intervention started within 2-weeks in people after stroke.
- 2. Estimate screening, recruitment and attrition rates, and reasons for declining participation or leaving the study early (where possible).
- 3. Estimate adherence/engagement to the SNMES protocol, including number of sessions completed/total sessions in treatment protocol

STIM-STROKE Protocol v1.0 30-04-2025

IRAS ID: 332116 Page **17** of **70**

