6.5. Responsibilities

Process for SAE

- 1. SAE identified
- 2. SAE CRF completed by a member of the research team
- 3. SAE CRF is sent to the local PI
- 4. Local PI will assess SAE for severity and causality and notify the CI of the SAE
- 5. The Sponsor will be made aware of the SAE within 24 hours of knowledge of the event via a member of the research team

Research practitioner

- Collecting data at study visit (Visit 2, 3, 4) regarding AE, AR, and SAE
- Reporting any AE, AR, SAE on the respective CRF
- Sending SAE CRF to local PI for evaluation

Principal Investigator (PI):

- Checking for SAEs when participants attend the study visit.
- Using medical judgement in assigning seriousness and causality.
- Ensuring that all SUSARs are recorded and reported to the sponsor within 24 hours of becoming aware of the event and provide further follow-up information as soon as available
- Ensuring that SUSARs are chased with Sponsor if a record of receipt is not received within 2 working days of initial reporting.

Chief Investigator (CI):

- Clinical oversight of the safety of study participants, including an on-going review of the risk / benefit.
- Immediate review of all SUSARs.

Sponsor:

- Central data collection and verification of adverse events according to the trial protocol onto a database.
- Using medical judgement to assign the SAE's seriousness and causality where it has not been possible to obtain local medical assessment – UHD Clinical Director for Research.
- Reporting safety information to Research Steering Group.
- Expedited reporting of SUSARs to the REC within required timelines.

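### Severity grading is required only for serious adverse events, so the expected non-serious reactions to stimulation carry no required grade

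*Protocol*

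**What the plan says.** Protocol section 6.1.8 sets the scope of severity grading: "The Investigator must assess the severity of Serious Adverse Events according to the following terms and assessments". The scale has three levels, the lowest being "Mild: Some discomfort noted but without disruption of daily life". The same section warns that an event's intensity is not the same thing as its seriousness.

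Section 6.5 keeps the same scope. Within the process for a serious event it says "Local PI will assess SAE for severity and causality and notify the CI of the SAE". The Principal Investigator's general duties are given as "Using medical judgement in assigning seriousness and causality", with no mention of severity.

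Causality is wider. Section 6.1.6 says "The Investigator must assess the causality of adverse events using their clinical judgement of the event", on a four-level scale from unrelated to definitely related.

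On what to expect, section 1.1 says "Common adverse events when they occur are skin irritation at the electrode site, muscle fatigue and soreness following electrical stimulation and joint pain". Section 6.1.1 lists reactions of this kind as examples of ordinary adverse events, beginning with "Skin redness, irritation, or rash at electrode site or from the brace". Section 6.1.7 anticipates no serious events.

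On use, section 2.3 says that "exploring/tracking adverse events and adverse reactions to treatment with SNMES" will contribute to determining feasibility and acceptability. Section 7.3 plans a descriptive summary of adverse events.

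**The concern.** The grade is required for the class of event that the protocol does not anticipate, and not for the class that it does. The expected reactions are mostly non-serious, and they are the ones named as informing whether the intervention is acceptable.

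The difference between brief redness under an electrode and a skin reaction or soreness that reduces normal activity is one of severity. If no grade is recorded at the time, it cannot be reliably reconstructed later. A statistical analysis plan can choose the tables, but it cannot tabulate a field that was never collected. That makes this a matter for the protocol.

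**Working it through.** No formula applies, because no stated figure depends on the severity rule. The check sets the sections side by side.

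| Item | Serious events | Non-serious events |
|---|---|---|
| Recorded on a case report form (6.5) | Yes | Yes |
| Causality assessed (6.1.6) | Yes | Yes |
| Severity grade required (6.1.8, 6.5) | Yes | Not stated |
| Anticipated by the protocol | No (6.1.7) | Yes (1.1, 6.1.1, Appendix 1) |

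**1. Is the restriction a slip in one sentence?** No. Section 6.5 follows 6.1.8: severity appears only in the serious-event steps and is absent from the Principal Investigator's general duties. Causality is not restricted in this way.

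**2. Does another section extend the grade?** No. Appendix 1 has the research team assess skin irritation, fatigue, soreness, joint pain and stimulation-site pain and respond to them, with checks at the initial session, week 6 and week 12. It sets no grade. Section 7.3 mentions no severity breakdown.

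**3. Which events are affected?** Section 6.1.1 gives seven examples of events that stimulation can cause: skin reaction, soreness, spasm, musculoskeletal injury, fatigue, strain and joint pain. None needs a grade unless it meets a seriousness criterion. Pressure sores or skin breakdown from the brace or stimulation are listed as serious in 6.1.2 and would be graded, so for skin the gap covers the lesser reactions.

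**4. Does the scale fit the events it is tied to?** Its lower two levels describe discomfort. That wording fits electrode redness or muscle soreness better than most of the serious examples in 6.1.2, such as myocardial infarction or pulmonary embolism.

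**5. How much exposure is involved?** Three sessions a week for 12 weeks is 3 × 12 = 36 sessions per participant. With 30 participants allocated to stimulation, that is 30 × 36 = 1,080 planned sessions. The protocol gives no reaction rate per session or per participant, so the number of ungraded events cannot be estimated.

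**6. What can the report show if the protocol is followed exactly?** Non-serious reactions by type and by relatedness (6.1.6), but not by severity.

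**The case against.** The strongest reply is that tolerability is well covered elsewhere.

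- Pain in the affected leg is scored 0 to 10 on a numerical or visual analogue scale at baseline, 6 weeks, 12 weeks and 6 months, in both arms.
- The session diary records how participants felt and why sessions were missed. Session number and duration are checked against the stimulator's log.
- Adherence is a progression criterion, and reasons for withdrawal are reported where available.
- Twelve stimulation participants and ten caregivers are interviewed, and clinicians take part in focus groups, using an acceptability framework.

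A reaction that limits use should show up in one of these. That much stands, and it rules out the reading, which someone might infer from 6.1.8, that the trial could not say whether stimulation is tolerable. It does not close the gap. The pain score belongs to a visit, not to a reported reaction. The diary and interviews give narrative without a standard grade. Neither skin irritation nor muscle fatigue has a scored outcome measure of its own.

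A second reply is that requiring a grade for serious events does not forbid one for others, and that the adverse event form is not shown. This also stands. A reader might infer that severity will be missing for every non-serious event, but the document does not establish that. It shows only that no grade is required.

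A third reply is that the scale is a poor instrument here. Participants cannot walk or transfer independently, so disruption of daily activities is confounded with the stroke itself. This is a fair limit on the remedy and is taken into the fix.

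Differing scopes for causality and severity are not a contradiction, and the point is not put as one.

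**Conclusion.** The point holds as a gap in a stated data-collection rule. Sections 6.1.8 and 6.5 require a grade for serious events only, while the reactions expected from stimulation, which contribute to the primary objective, are mainly non-serious. Followed as written, the protocol supports a summary of these reactions by type and relatedness but not by severity.

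The consequence is modest. Table 3 has no adverse-event or tolerability criterion, so a reader who infers that these grades decide progression would be wrong: event tracking contributes to the judgement and does not settle it. Nor would the report be confined to bare counts, since causality is assessed for all adverse events. The target of 60 participants and the planned analyses are unaffected.

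The conclusion assumes that the case report form adds nothing to the protocol text. If it already has a severity field for all events, only the wording of 6.1.8 and 6.5 needs to change.

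**What to change.** 1. In 6.1.8, change the scope of grading from serious adverse events to all adverse events.
2. In 6.5, add severity of all adverse events to the Principal Investigator's duties, so that the two sections agree.
3. Confirm that the adverse event form carries the three-level grade, and add it if it does not.
4. Show the descriptive summary in 7.3 by type, severity and relatedness.
5. State in 6.1.8 that the grade reflects the change attributable to the event, over and above the limitation already caused by the stroke. Without this, the daily-activity wording could push grades upwards for reasons unrelated to stimulation.

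The cost is one field per event, a short judgement by the investigator, and two small wording changes. No visit, treatment rule or sample size changes. Even with step 5, the scale will be a coarse measure in this population.
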